8.10 Biomarkers

Biomarkers are not evaluated in this study.

8.11 Health Economics Medical Resource Utilization and Health Economics

Medical Resource Utilization and Health Economics are not evaluated in this study.

8.12 Visit Requirements

Visit requirements are outlined in Section 1.3. Specific procedure-related details are provided in Section 8.

8.12.1 Screening

Approximately 4 weeks prior to treatment allocation, potential participants will be evaluated to determine that they fulfill the entry requirements as set forth in Section 5.

Participants may be rescreened after consultation with the Sponsor. Rescreening should include all screening procedures listed in the SoA, including consent review. Rescreen procedures cannot be conducted the day prior to treatment allocation if there are Day -1 procedures planned per protocol.

8.12.2 Treatment Period Visit

8.12.2.1 Predose Procedures (All Panels)

Prior to each treatment, the clinical and laboratory safety data, viral load data, and PK data from the previous dose level/treatment panel will be reviewed by the Investigator and the Clinical Team and a mutual decision on whether to advance to the next dose level will be made. No dose escalation will occur without agreement of the Investigator and the Sponsor.

Participants will report to the CRU the day prior to the scheduled day of administration of the study drug or time specified by the investigator. Participants will fast from all food and drink, except for water, for a minimum of 8 hours prior to study drug administration and prior to obtaining samples for laboratory safety tests (refer to Section 5.3).

After the Day 1 predose procedures have been completed, participants will be assigned a unique allocation number associated with a specific treatment sequence as defined by a computer-generated allocation schedule. For details on procedures, please refer to the SoA (Section 1.3), Procedures (Section 8) and/or corresponding appendices.

8.12.2.2 Treatment Procedures (All Panels)

Procedures for study drug administration and postdose procedures are listed in the SoA, Section 1.3 of this protocol.

Participants will be administered a single dose of MK-8527 in the morning. The exact clock time of dosing should be recorded.

8.12.3 Discontinued Participants Continuing to be Monitored in the Study

At any point if a participant discontinues from treatment but continues to be monitored in the study, all study procedures specified in the SoA may be completed at the discretion of the investigator and with Sponsor agreement. The subset of study procedures completed will be communicated in a protocol clarification letter.

8.12.4 Poststudy

Participants will be required to return to clinic approximately 28 days after the last dose of study intervention for the poststudy visit. If the poststudy visit occurs less than 28 days after the last dose of study intervention, a subsequent follow-up telephone call should be made at 28 days post the last dose of study intervention to determine if any AEs have occurred since the poststudy clinic visit.

8.12.5 Critical Procedures Based on Study Objectives: Timing of Procedure

For this study, the VL and PBMC blood sample for MK-8527 are the critical procedures.

At any postdose time point, the PBMC blood sample for MK-8527 needs to be collected as close to the exact time point as possible. All other procedures should be completed as close to the prescribed/scheduled time as possible. Study procedures can be performed prior or after the prescribed/scheduled time.

The order of priority can be changed during the study with joint agreement of the investigator and the Sponsor Clinical Director.

Any nonscheduled procedures required for urgent evaluation of safety concerns take precedence over all routine scheduled procedures.

The following variance in procedure collection times will be permitted.

- PK Collection (MK-8527 plasma and MK-8527-TP PBMC) and PD collection (viral load) as outlined in [Table 8](#).

Table 8 PK/PD Blood Collection Window

| Blood PK/PD Collection | PK/PD Collection Window |
|------------------------|-------------------------|
| 0 – 1.0 hr | 5 min |
| 1 - <2hr | 10 min |
| 2 - <24 hr | 15 min |
| 24 - <48 hr | 1 hr |
| 48 - 168 hr | 2 hr |
| >168 - <672 hr | 24 hr |
| 672 hr | 48 hr |

- Predose standard safety evaluations: VS and ECG at 3 hrs; laboratory safety tests, urine drug screen and physical exam at 24 hrs
- Postdose standard safety evaluations: VS, ECG, laboratory safety tests, and physical exam
 - a. <24 hr postdose may be obtained within 15 min of the theoretical sampling time
 - b. 24 hr - <48 hr postdose may be obtained within 1 hr of the theoretical sampling time
 - c. 48 hr – 168 hr postdose may be obtained within 2 hr of the theoretical sampling time
 - d. >168 - <672 hr postdose may be obtained within 24 hr of the theoretical sampling time
 - e. 672 hr postdose may be obtained within 48 hr of the theoretical sampling time

8.12.6 Study Design/Dosing/Procedures Modifications Permitted Within Protocol Parameters

This is a Phase 1 assessment of MK-8527 in humans, and the PK, PD, and safety profiles of the compound are still being elucidated. This protocol is written with some flexibility to accommodate the inherent dynamic nature of Phase 1 clinical studies. Modifications to the dose, dosing regimen, and/or clinical or laboratory procedures currently outlined may be required to achieve the scientific goals of the study objectives and/or to ensure appropriate safety monitoring of the study participants.

As such, some alterations from the currently outlined dose and/or dosing regimen may be permitted based on newly available data, but the maximum daily dose may not exceed that that tested in Protocol 001.

- Repeat of or decrease in the dose of the study intervention administered in any given panel
- Entire panel(s) may be omitted
- Adjustment of the dosing interval (e.g., divided doses [BID to QD, QD to BID, TID, or vice versa])
- Instructions to take study intervention with or without food or drink may also be modified based on newly available data
- Modification of the PK/pharmacodynamic sample timing, processing and shipping details based on newly available data

The PK/PD sampling scheme currently outlined in the protocol may be modified during the study based on newly available PK or PD data (e.g., to obtain data closer to the time of peak plasma concentrations). If indicated, these collected samples may also be assayed in an exploratory manner for metabolites and/or additional PD markers.

Up to additional 50 mL of blood may be drawn for safety, PK, and/or PD analyses. The total blood volume withdrawn from any single participant will not exceed the maximum allowable volume during his/her participation in the entire study (Section 8).

The timing of procedures for assessment of safety procedures (e.g., VS, ECGs, safety laboratory tests, etc.) may be modified during the study based on newly available data. Additional laboratory safety tests may be added to blood samples previously drawn to obtain additional safety information. These changes will not increase the number of study procedures for a given participant during his/her participation in the entire study.

It is understood that the current study may employ some or none of the alterations described above. Any alteration made to this protocol to meet the study objectives must be detailed by the Sponsor in a letter to the Study file and forwarded to the investigator for retention. The letter may be forwarded to the IRB/IEC at the discretion of the investigator.

9 STATISTICAL ANALYSIS PLAN

9.1 Statistical Analysis Plan Summary

This section contains a brief summary of the statistical analyses for this trial. Full detail is in the Statistical Analysis Plan (SAP) (Sections 9.2-9.9).

Statistical Methods

Primary Objective (Safety): Incidence of AEs will be descriptively summarized. Summary statistics and plots will be generated for the change from baseline values in the VS, ECG parameter values, and selected laboratory safety parameter values for participants, as deemed clinically appropriate. Depending on the safety parameter, the difference from baseline will either be computed on the original scale (raw change from baseline) or on the log scale and back-transformed for reporting (percent change from baseline). Summary statistics for the raw laboratory safety tests, ECGs, and/or VS may also be computed, as deemed clinically appropriate.

Primary Objective (Pharmacodynamics): The log₁₀ plasma HIV-RNA (copies/mL) measurements from participants in all panels will be pooled and analyzed based on a longitudinal data analysis model containing fixed effects for dose level, time (pre-dose, 168 hrs post-dose) and dose level by time interaction, and a random effect for participant. The change from baseline for each dose level at 168 hours post-baseline will be estimated from this model. A posterior distribution for the true mean change from baseline at 168 hours will be generated for each dose level using flat priors under a normal likelihood assumption. Historical placebo data from recent monotherapy studies in HIV-1 participants (MK-0518 Protocol 004, MK-1439 Protocol 005, MK-6186 Protocol 007, and MK-1972 Protocol 003) will be separately analyzed based on a longitudinal data analysis model containing fixed effects for study and time (pre-dose, 168 hours post-dose), and a random effect for participant. The change from baseline for placebo at 168 hours post-baseline will be estimated from this model, and a posterior distribution for the true mean change from baseline at 168 hours will be generated using flat priors under a normal likelihood assumption. Using the posterior distributions for each dose level and placebo, the posterior distribution of the true mean difference between each dose level and placebo will be generated, and the posterior probability that the true mean difference in the log₁₀ plasma HIV-1 RNA reduction from baseline between MK-8527 and placebo is at least 1.0 log₁₀ copies/mL will be calculated. A 70% posterior probability for at least one dose level that also exhibits an acceptable safety and tolerability profile will satisfy the primary pharmacodynamics hypothesis. For each dose level, the posterior probability that the true mean log₁₀ plasma HIV-1 RNA reduction from baseline is at least 1.0 log₁₀ copies/mL will also be calculated.

9.2 Responsibility for Analyses

The statistical analysis of the data obtained from this study will be conducted by, or under the direct auspices of, the Early Clinical Development Statistics Department in collaboration with the Quantitative Pharmacology and Pharmacodynamic Department and Translational Pharmacology Department of the Sponsor.

If, after the study has begun, changes are made to the statistical analysis plan stated below, then these deviations to the plan will be listed, along with an explanation as to why they occurred, in the Clinical Study Report.

9.3 Hypotheses/Estimation

Primary

At a dose that is sufficiently safe and generally well tolerated, MK-8527 has superior antiretroviral activity compared to placebo, as measured by change from baseline in plasma HIV-1 RNA (log₁₀ copies/mL) at 168 hours postdose. That is, the true mean difference in the plasma HIV-1 RNA reduction from baseline between MK-8527 and placebo is at least 1.0 log₁₀ copies/mL.

Secondary

At a dose that is sufficiently safe and generally well tolerated, the true GM C_{168hr} MK-8527-TP in PBMC is at least 0.2 pmol/10⁶ cells.

9.4 Analysis Endpoints

Primary Pharmacodynamic

The primary pharmacodynamic variables in this study include plasma HIV -1 RNA pre-dose and 4, 24, 96, 120, 144, 168, 240, 336, 504 and 672 hours post-dose.

Primary Safety

The primary safety endpoints in this study include all types of AEs, in addition to laboratory safety assessments, ECGs, and VS.

Secondary Endpoints

The secondary endpoints in this study include AUC_{0-168hr}, T_{max}, C_{max}, C_{168hr}, apparent terminal t_{1/2} for both MK-8527 plasma and MK-8527-TP in PBMC following single oral administration of MK-8527 on Day 1.

9.5 Analysis Populations

The following populations are defined for the analysis and reporting of data. All participants will be reported, and their data analyzed, according to the treatment(s) they actually received.

All Participants as Treated (ASasT) – The population includes all participants who received at least one dose of the investigational drug. This population will be used for assessments of safety and tolerability.

Per-Protocol (PP) – The population includes the subset of participants who comply with the protocol sufficiently to ensure that generated data will be likely to exhibit the effects of treatment, according to the underlying scientific model. Compliance covers such considerations as exposure to treatment, availability of measurements and absence of major protocol deviations. Major protocol deviations will be identified to the extent possible prior to unblinding by individuals responsible for data collection/compliance, and its analysis and interpretation. Any participants or data values excluded from analysis will be identified, along with their reason for exclusion, in the CSR. At the end of the study, all participants who are compliant with the study procedure as aforementioned and have available data from at least one treatment will be included in the primary analysis dataset. This population will be used for the primary PD, secondary PK and exploratory PK and PD analyses.

9.6 Statistical Methods

Primary (Safety)

Incidence of AEs will be descriptively summarized. Summary statistics and plots will be generated for the change from baseline values in the VS, ECG parameter values, and selected laboratory safety parameter values for participants, as deemed clinically appropriate. Depending on the safety parameter, the difference from baseline will either be computed on the original scale (raw change from baseline) or on the log scale and backtransformed for reporting (percent change from baseline). Summary statistics for the raw laboratory safety tests, ECGs, and/or VS may also be computed, as deemed clinically appropriate.

Primary (Pharmacodynamics)

The log₁₀ plasma HIV-RNA (copies/mL) measurements from participants in all panels will be pooled and analyzed based on a longitudinal data analysis (LDA) model containing fixed effects for dose level, time (pre-dose, 168 hrs post-dose) and dose level by time interaction, and a random effect for participant. The response vector consists of the baseline and 168 hours post-baseline values. Time is treated as a categorical variable so that no restriction is imposed on the trajectory of means over time. The change from baseline for each dose level at 168 hours post-baseline will be estimated from this model. A posterior distribution for the true mean change from baseline at 168 hours will be generated for each dose level using flat priors under a normal likelihood assumption.

Historical placebo data from recent monotherapy studies in HIV-1 participants (MK-0518 Protocol 004, MK-1439 Protocol 005, MK-6186 Protocol 007, and MK-1972 Protocol 003) will be separately analyzed based on a longitudinal data analysis model containing fixed effects for study and time (pre-dose, 168 hrs post-dose), and a random effect for participant. The change from baseline for placebo at 168 hours post-baseline will be estimated from this model, and a posterior distribution for the true mean change from baseline at 168 hours will be generated using flat priors under a normal likelihood assumption. Using the posterior distributions for each dose level and placebo, the posterior distribution of the true mean difference between each dose level and placebo will be generated, and the posterior probability that the true mean difference in the log₁₀ plasma HIV-1 RNA reduction from baseline between MK-8527 and placebo is at least 1.0 log₁₀ copies/mL will be calculated.

A 70% posterior probability for at least one dose level that also exhibits an acceptable safety and tolerability profile will satisfy the primary pharmacodynamics hypothesis. For each dose level, the posterior probability that the true mean log₁₀ plasma HIV-1 RNA reduction from baseline is at least 1.0 log₁₀ copies/mL will also be calculated. To address the exploratory objective related to antiretroviral activity at 672 hours post-baseline, a similar analysis will be performed using VL measurements at baseline and 672 hours post-baseline. Similar exploratory analyses may be performed at timepoints earlier than 168 hours post-baseline.

Secondary (Pharmacokinetic)

Values of MK-8527 plasma and intracellular MK-8527-TP in PBMC pharmacokinetic parameters C_{168hr}, C_{336hr}, C_{672hr}, AUC_{0-168hr}, AUC_{0-last}, AUC_{0-inf}, and C_{max} from participants in all panels will be pooled. Each PK parameter will be analyzed separately for plasma and PBMC. The PK log transformed and analyzed based on a linear model containing a fixed effect for dose level. The 95% confidence intervals for the means will be constructed on the natural log scale and will reference the t-distribution. Exponentiating the means will yield estimates for the population geometric means on the original scale. The secondary hypothesis will be evaluated by calculating the posterior probability that the true GM C_{168hr} MK-8527-TP in PBMC is at least 0.2 pmol/10⁶ cells for each dose level using flat priors under a normal likelihood assumption. The secondary hypothesis will be supported for any dose for which the posterior probability is greater than 70%. Data will be examined for departures from the assumptions of the statistical model(s) as appropriate; e.g., heteroscedasticity, nonnormality of the error terms. Distribution-free methods may be used if a serious departure from the assumptions of the model(s) is observed, or suitable data transformation may be applied.

Individual values will be listed for each MK-8527 plasma and intracellular MK-8527-TP in PBMC PK parameter (C_{168hr}, C_{240hr}, C_{336hr}, C_{540hr}, C_{672hr}, AUC_{0-168hr}, AUC_{0-last}, AUC_{0-inf}, C_{max}, T_{max}, and apparent terminal t_{1/2}) by dose level, and the following (non-model-based) descriptive statistics will be provided: N (number of participants with non-missing data), arithmetic mean, standard deviation, arithmetic percent CV (calculated as 100 x standard deviation/arithmetic mean), median, minimum, maximum, geometric mean, and geometric percent CV (calculated as 100 x sqrt(exp(s²) - 1), where s² is the observed variance on the natural log-scale).

Secondary and Exploratory (Pharmacokinetic/Pharmacodynamic)

The PK-PD and dose-PD association of MK-8527 will be explored. Graphs to visualize the association of the reduction in log₁₀ plasma HIV-1 RNA levels with various plasma and intracellular MK-8527-TP in PBMC parameters (e.g., C_{168hr}, C_{672hr}, AUC_{0-168hr}, AUC_{0-last}, AUC_{0-inf}, and C_{max}) and dose will be generated. Exploratory linear and/or non-linear model fits may be considered, as appropriate. Exposure levels and doses that result in various proportions of the population (e.g., 80%, 90%) that have at least 1.0 log₁₀ reduction from baseline in plasma HIV-1 RNA levels with high confidence may be estimated.

The duration of antiretroviral suppression after a single dose of MK-8527 will be evaluated with individual plots across time.

9.7 Interim Analyses

No interim analysis is planned in this study.

9.8 Multiplicity

Since there is only one primary pharmacodynamic hypothesis, no multiplicity adjustment will be made.

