1.2 Schema

The study design is depicted in [Table 1](#).

Table 1 Dose Escalation Scheme for MK-8527

| Panel ^a | Dose of MK-8527 ^b | | | | |
|--------------------|------------------------------|-------|--------|--------|--------|
| A | 10 mg | | | | |
| B | | 25 mg | | | |
| C ^c | | | ≤50 mg | | |
| D ^c | | | | ≤50 mg | |
| E ^c | | | | | ≤50 mg |

^a In each panel, 6 participants will receive a single dose of MK-8527.

^b The decision to proceed to the next panel will be made following review of safety and viral load data out to at least Day 8 (i.e., 7 days post-dose) from the preceding panel.

^c A decision to enroll Panel C and the dose to be administered will be based on the results of safety, PK and viral load data out to at least Day 8 in Panels A and B. Enrollment of Panels D and E and the doses to be administered will be based on the results of safety, PK, and viral load data from all prior panels.

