4.2.1.3 Viral Pharmacodynamic Endpoints

A pharmacodynamic (PD) endpoint of a $>1.0 \log_{10}$ suppression of HIV-1 RNA from baseline on Day 7, relative to historical placebo data, will be used. A 70% posterior probability of achieving the target viral load reduction for at least one dose level that also exhibits an acceptable safety and tolerability profile will satisfy the primary pharmacodynamic hypothesis. The 70% posterior probability was chosen as a reasonable level of certainty in the results to ensure that the appropriate dose(s) that can achieve the PD target is taken into subsequent studies in the patient population with a reasonable chance of achieving the desired therapeutic effect in VL reduction. This target is consistent with previous observations with NRTI drugs which have produced VL reduction of $0.5 \log_{10}$ as well as results with some newer compounds which have demonstrated potential to lower VL below $1.0 \log_{10}$, and also with past feedback from regulatory agencies that limit NRTI monotherapy studies to 7-10 days in duration. A decrease of this magnitude supports potential activity with long term administration in the target population.

Participants with a baseline HIV-1 RNA load of at least 5,000 copies/mL will be enrolled to ensure an adequate dynamic range by which changes in HIV RNA can be quantified. Periodic blood samples will be collected to assess MK-8527 associated changes in absolute VL over time and will be compared relative to historical placebo data. Based on the long half-life of MK-8527-TP, changes in VL may be assessed through 28 days for participants who do not initiate follow-on ART. For these participants, any VL data that are further collected as part of routine follow-up may be transmitted to the Sponsor, provided the participant gave appropriate consent. These extra data would only be reviewed to determine when the participant's VL returned to baseline to provide an exploratory and preliminary understanding of the long term effect of MK-8527.

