4.3.1 Starting Dose for This Study

The ongoing Phase 1 study in healthy participants (Protocol 001) is exploring the safety, tolerability and PK of MK-8527. The goal is to establish the safety of MK-8527 in humans and to determine if the projected PK target for MK-8527 could be achieved at a dose that is well tolerated in humans.

The study has explored single doses up to 100 mg. It has been generally well tolerated with only mild AEs reported and no serious AEs observed. [REDACTED]

This study is intended to evaluate the VL reduction potential of MK-8527 in ART-naïve HIV infected individuals. The PK profile of MK-8527 in this target participant population is unknown at this time and it is unclear if it is similar to the profile in healthy participants. To avoid the potential of underdosing in the participant population, a starting dose of 10 mg is being proposed. In Protocol 001, the PK target was achieved in healthy participants who received a dose of 5 mg. This minimizes the risk of exposing HIV-1 infected participants to drug levels below what are predicted to provide adequate VL reduction.

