9.9 Sample Size and Power Calculations

Pharmacodynamic (Primary): If the true SDs of the log₁₀ reduction from baseline in plasma HIV-RNA at 168 hours postdose are 0.3, 0.4, or 0.5 for this study, there is ~80% power to yield at least 70% posterior probability if the true mean log₁₀ reduction is at least 1.11, 1.12, or 1.13 log₁₀ with N=6 participants in a panel.

PK

Pharmacokinetic (Secondary): If the true SDs of the C_{168hr} triphosphate in PBMC are 0.25, 0.35, or 0.45 for this study, there is ~80% power to yield at least 70% posterior probability if the true mean C₁₆₈ are at least 0.27, 0.27, or 0.28 pmol/10⁶ cells with N=6 participants in a panel.

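### Does the reason in 9.8 for making no multiplicity adjustment overlook that any of up to five dose levels can meet the primary hypothesis?

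*Combined protocol and SAP*

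**What the plan says.** The primary hypothesis (9.3) is that, at a dose with adequate safety, the true reduction in plasma HIV-1 RNA at 168 hours exceeds that on placebo by at least 1.0 log10 copies/mL. The success rule in 9.6 reads: "A 70% posterior probability for at least one dose level that also exhibits an acceptable safety and tolerability profile will satisfy the primary pharmacodynamics hypothesis". Sections 9.1 and 4.2.1.3 repeat it.

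On multiplicity, 9.8 contains one sentence: "Since there is only one primary pharmacodynamic hypothesis, no multiplicity adjustment will be made".

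The secondary PK hypothesis has a 70% cut-off too, but is judged dose by dose: "The secondary hypothesis will be supported for any dose for which the posterior probability is greater than 70".

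Section 9.9 gives power for a single panel only, "with N=6 participants in a panel". Section 4.1 allows up to five panels, and how many are run depends on what the earlier panels show: "Enrollment of Panels D and E and the doses to be administered will be based on the results of safety, PK, and viral load" (Table 1, note c). Section 4.2.1.3 explains the 70% cut-off as a way to ensure that "the appropriate dose(s) that can achieve the PD target is taken into subsequent studies".

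**The concern.** Section 9.8 counts hypotheses, but multiplicity here comes from the number of ways to meet one hypothesis. If any of several dose levels can satisfy it, the chance that at least one does so exceeds the chance for each dose. The plan shows no rate for the study-level rule when no dose truly reaches 1.0 log10.

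The effect is greatest when all doses respond alike, and that cannot be excluded. Section 4.3.1 states: "In Protocol 001, the PK target was achieved in healthy participants who received a dose of 5 mg". Panel A starts above that, at 10 mg, so every panel could lie on a plateau. If the plateau were just short of target, a bare statement that the hypothesis was met would mean less after five dose levels than after one, and a reader could not tell how much less. At stake would be the weight given to that statement when a dose is taken into later studies.

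**Working it through.** **Inputs.** Target 1.0 log10 and 70% cut-off (9.6); flat prior and normal likelihood (9.6); SD 0.3, 0.4 or 0.5 and 6 participants per panel (9.9); up to five panels (4.1). The size of the historical placebo group is not in the documents, so its error is ignored at first.

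**Pass chance for one dose level.** With a flat prior, a dose passes when its estimate exceeds 1.0 by 0.524 standard errors. For a true difference d, with SE = SD/√6:

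p = Φ((d − 1.0)/SE − 0.524)

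**The plan's own figure first.** Section 9.9 gives about 80% power at true means of 1.11, 1.12 and 1.13 for SD 0.3, 0.4 and 0.5. The formula gives 65%, 58% and 54%; 80% would need means of about 1.17, 1.22 and 1.28. The stated power is not reproduced. That is a separate question; only the SD and N from 9.9 are used below.

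**Any of k dose levels, equal response.** The chance is 1 − (1 − p)^k. For d = 0.9 and SD 0.4, SE = 0.4/√6 = 0.1633 and p = Φ(−0.612 − 0.524) = 12.8%. For five levels, 1 − 0.872^5 = 49.5%.

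| True difference at every dose (SD 0.4) | k=1 | k=2 | k=3 | k=4 | k=5 |
|---|---|---|---|---|---|
| 0.8 | 4% | 8% | 12% | 15% | 19% |
| 0.9 | 13% | 24% | 34% | 42% | 50% |
| 1.0 (hypothesis just true) | 30% | 51% | 66% | 76% | 83% |

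At 0.9, SD 0.3 gives 9% for one level and 38% for five; SD 0.5 gives 16% and 57%.

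**Shared placebo estimate.** Simulation with pooled variance, SD 0.4 and an assumed placebo N of 20 to 60 gives 14 to 15% for one level and 47 to 49% for five at 0.9.

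**Graded response.** For d = 0.5, 0.6, 0.7, 0.8 and 0.9, p is about 0.02%, 0.15%, 0.9%, 4.0% and 12.8%. Then 1 − (0.9998 × 0.9985 × 0.991 × 0.960 × 0.872) = 17%, against 13% for the top dose alone.

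**Repeated doses.** The model has an effect per dose level, so panels at the same dose share one level. If Panels C to E used one dose (18 participants), its pass chance at 0.9 would be 5.6%, and the any-dose chance would be 1 − 0.872² × 0.944 = 28%.

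**Correct passes.** At a true 1.12 with SD 0.4, one level passes in 58% of trials, at least one of three in 93%, and at least one of five in 99%.

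**What the plan already produces.** Sections 9.1 and 9.6 call for the posterior probability of a difference from placebo of at least 1.0 log10 for each dose level, and a second probability per dose level for the reduction from baseline. The 12.8% for a given dose at 0.9 is the same whether one or five levels are tested.

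**The case for a change.** The strongest case for a change is that the stated reason misses the point, that 9.9 itself judges the rule by its long-run pass rate, and that the same rate below target is therefore a fair thing to ask for. Wording the primary verdict by dose, as the secondary one is worded, and adding a small table would cost little. Stopping once a dose succeeds, which 4.4.1 permits, does not remove the effect, because going on after failures is how the chance builds up.

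Most of this stands as description. The sentence in 9.8 is formally true, since the hypothesis is about the existence of a dose, but it does not discuss the any-dose rule. The case weakens at the remedy:

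- A verdict by dose would relabel probabilities that the plan already calculates.
- A rate for the number of levels actually tested would not describe the design, because that number depends on viral load results. A trial that stopped after its first dose passed would show 13%, although it could have gone on to five.
- Editing 9.6 and 9.8 alone would leave the any-dose rule standing in 9.1 and 4.2.1.3.
- A stricter cut-off would change results. Holding the any-of-five rate at 12.8% in the 0.9 scenario would need a cut-off of about 0.91 per dose, at the price of correct passes. The concern itself does not ask for this.

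**Conclusion.** No change to the plan is needed. The reason in 9.8 is incomplete, but the gap is one of explanation. The any-dose chance is real: about 13% for one level and at most about 50% for five when every dose truly gives 0.9 log10. The upper figure assumes five distinct doses, equal response, acceptable safety at all of them, SD 0.4, 6 participants per level and negligible placebo error; the 0.9 is illustrative. It falls to about 17% with a graded response and to 19% with five equal doses at 0.8.

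The inflation touches only the study-level label. Decisions to advance rest on individual doses, whose probabilities will be calculated. An analyst reporting the trial would naturally show all of them and say how many doses were tested. Giving the Phase 1 dose-selection purpose as the reason in 9.8, with a design-level rate for up to five doses, would be courteous to readers but would alter no analysis, cut-off or result. The lenient rule trades more near-miss passes for fewer missed active doses, which is defensible at this stage. The power figure in 9.9 that does not reproduce is a different matter and is not settled here.
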